7.3 PCR for bcl-2

7.3.1 PCR in the peripheral blood will be followed every 3-4 months during the first 18 months, then every 6 months until month 36, then every 12 months. PCR in the bone marrow will be followed at times of bone marrow sampling, (see Section 7.2.1 and Appendix E), i.e., baseline, before Zevalin, 6-8 weeks after Zevalin, at months 9 and 12, and then every 4-6 months during the first 3 years, and every 12 months subsequently.

7.3.2 For patients who are still PCR positive after Zevalin: proceed to rituximab and explore alternative (off this protocol) treatment options, especially stem cell transplant, which is recommended to be pursued at first evidence of progressive disease by clinical (x-ray, marrow, physical exam) criteria.

7.4 Recommended: Restaging after month 12: every 4 months for 1 year (while on maintenance), then every 4-6 months for 2 years, then yearly (see Appendix E). Beyond year 5, it is recognized that these recommended assessments may not be realistic (due to age, distance, or cost issues). We will nonetheless strive to get this data.

7.5 Optional: Peripheral blood lymphocyte surface markers and Ig's every 3-4 months during therapy, and every 6-12 months off therapy until any abnormalities resolve.

7.6 Marrow cytogenetics: after 4 courses R-FND (before Zevalin): and 12-18 months after Zevalin.

7.7 During Zevalin phase:

- CBC, diff, platelets weekly x 12 wks;
- chemistries monthly x 3 mo;
- urinalysis at 1 and 3 mo;
- immunoglobulins at 3 mo;

• HAMA at times of lab testing/clinic visits post-Zevalin (see Section 7.2), i.e., at about 6-8 weeks after Zevalin, and at months 9 and 12.

7.8 During rituximab maintenance: CBC with differential and SMA every 1-3 months during maintenance

7.9 Outside Physician Participation During Treatment (Some general information regarding outside physician participation can also be found in Appendix G).

7.9.1 MDACC Physician communication with the outside physician is required prior to the patient returning to the local physician. This will be documented in the patient record

7.9.2 A letter to the local physician outlining the patient's participation in a clinical trial will request local physician agreement to supervise the patient's care (Appendix M) and a copy of the chemotherapy instructions will also be sent to the outside physician (Appendix N).

7.9.3 Protocol required evaluations outside MDACC will be documented by telephone, fax or e-mail. Fax and/or e-mail will be dated and signed by the MDACC physician, indicating that they have reviewed it.

7.9.4 Changes in drug dose and/or schedule must be discussed with and approved by the MDACC physician investigator, or their representative prior to initiation, and will be documented in the patient record.

7.9.5 A copy of the informed consent, protocol abstract, treatment schema and evaluation during treatment will be provided to the local physician.

7.9.6 Documentation to be provided by the local physician will include drug administration records, progress notes, reports of protocol required laboratory and diagnositic studies and documentation of hospitalizations.

7.9.7 The home physician will be requested to report to the MDACC physician investigator all life threatening events within 24 hours of documented occurrence.

7.9.8 Patients will return to MDACC at least every 2-3 cycles for evaluation.

7.9.9 Physician to physician communication regarding protocol enrollment is required prior to the patient returning to the home physician and documentation of these conversations must be documented in the patient record.

7.9.10 A letter to the home physician outlining the patient's participation and requesting the home physician agreement to supervise the patient's care. The letter will be approved by the IRB as part of the protocol and a copy will be provided to the patient. (a copy of this letter can be found in Appendix M, and a copy of the chemotherapy instructions will also be sent to the outside physician (Appendix N).

7.9.11 The following documents are to be provided to the outside physician:

- a copy of the informed consent
- the protocol abstract

- the protocol treatment schema

- the protocol "Evaluation During Treatment" section

7.9.12 Communication of protocol required evaluations to MDACC investigators can be by telephone (dictation documentation required), fax, or e-mail. Authentication of fax and/or e-mail documents requires date and physician signature. This becomes part of the source documentation in the medical record.

7.9.13 The informed consent will describe the outside physician participation.

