5.6.2 For all other toxicities (see Appendix B)

G	ra	de	
			-

- 0-2 No change
- 3 Decrease one level
- 4 Stop Treatment
- 5.6.3 Duration of therapy and intervals between courses:
- a) R-FND courses are recommended to repeated every 28 days, after verification of hematologic recovery.

b) Total length of R-FND treatment will be 4 courses for most patients. Exceptions should be discussed with PI, e.g. give more if response is slow (see sections 5.1.5 and 5.1.8), or stop early if there is evidence of cumulative myelosuppression, with more than 6 weeks before recovery of granulocytes to 1000 or more or platelets to 100,000 or more.

5.6.4 Patients older than 60 years will receive full doses of chemotherapy.

5.6.5 Anyone experiencing delayed recovery of granulocyte counts (>35 days) or neutropenic fever will be candidates for colony stimulating factor support, with the chemotherapy doses adjusted down one dose level.

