8.4 **Reporting of Serious Adverse Events to the Principal Investigator, the IRB and, if necessary, the FDA** any serious or unexpected adverse event (including death) due to any cause whether or not related to the study drug(s) must be immediately reported to the principal investigator.

It is the responsibility of the Investigator-Sponsor as the IND holder to **IMMEDIATELY REPORT ALL SERIOUS OR UNEXPECTED ADVERSE EVENTS IMMEDIATELY TO THE IRB CHAIR (AS PER INSTITUTION POLICY) AND, IF APPROPRIATE, TO THE FDA BY COMPLETING AND SUBMITTING A MEDWATCH FORM (FDA FORM 3500A).** The Investigator-Sponsor must promptly provide a copy of the MedWatch form to IDEC Pharmaceutical Corporation at the same time it is submitted to the FDA. **Completed FDA 3500A reports should be faxed to the Pharmacovigilance Department of IDEC Pharmaceuticals Corporation [contact]).** See Appendix A and M for additional information and a blank copy of the MedWatch form.

Serious adverse events occurring after initiation of other anti-cancer therapy do not need to be reported, unless the therapy is initiated and the event occurs within 30 days following the infusion of the study drug or the event is felt to be related to the study drug. All written IND Safety Reports submitted to the FDA by the Sponsor-Investigator must also be faxed to:

Genentech Drug Safety [contact] [contact] or [contact]

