10.2. Secondary objectives

Additional endpoints are achievement of response (CR + CRu + PR), as defined in Section 8, overall survival, and safety. Toxicity will be recorded for all patients, separately by grade, type of toxicity, and chemotherapy cycle. For patients treated with Zevalin, subsequent toxicity, including HAMA, will be tabulated separately.

Concerning safety, the R-FND therapy program is known to be safe (24). The use of Zevalin is safe (33,35). The sequential use of Zevalin shortly after chemotherapy is innovative, but not unprecedented ([name], personal communication). The potential for marrow toxicity will be monitored carefully following Zevalin (see Section 7.7).

Treatment related mortality is expected to be rare. Any such events will be reported (see Section 11.4); if 2 or more treatment related deaths occur, the study will be temporarily placed on hold, and discussion about early closure will take place.

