# **11.0 Data and Protocol Management, and Reporting**

11.1 Protocol Compliance: The attending physician and oncology research nurse must be in contact with (and preferably see) each patient at least every 2-3 cycles. All required interim and pretreatment data should be available and the physician must have made a designation as to tumor response and toxicity grade. All requirements of the MDACC protocol for outside physician participation must be adhered to (see Appendix G).

11.2 Data Entry: Data must be entered into the Protocol Data Management System. A brief explanation for required but missing data should be recorded as a comment.

11.3 Accuracy of Data Collection: The Study Chairman will be the final arbiter of response of toxicity should a difference of opinion exist.

11.4 Any life-threatening and/or unexpected and serious (Grade 3 or 4) toxicity will be reported immediately to the Study Chairman who, in turn, must notify the Surveillance Committee and the sponsors.

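### Section 7.9.7 asks home physicians only for life-threatening events, so other serious events have no stated deadline from them, although 8.4 and 11.4 require immediate reporting

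*Combined protocol and SAP*

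**What the plan says.** Outside physicians may supervise treatment between visits to the centre (Section 7.9). For expedited reporting, 7.9.7 states: "The home physician will be requested to report to the MDACC physician investigator all life threatening events within 24 hours of documented occurrence". Section 7.9.6 also has the local physician supply drug administration records and "progress notes, reports of protocol required laboratory and diagnositic studies and documentation of hospitalizations", with no time limit. Section 7.9.8 adds: "Patients will return to MDACC at least every 2-3 cycles for evaluation".

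The trial-wide rules are broader. In 8.4 the recipient is the principal investigator, and the rule is that "any serious or unexpected adverse event (including death) due to any cause whether or not related to the study drug(s) must be immediately reported". The investigator-sponsor must then report at once to the IRB and, where appropriate, the FDA. Section 11.4 says: "Any life-threatening and/or unexpected and serious (Grade 3 or 4) toxicity will be reported immediately to the Study Chairman".

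Sections 7.9.5 and 7.9.11 list what the outside physician receives: the consent form, the abstract, the treatment schema and the section on evaluation during treatment. That last item appears to be Section 7.0, which contains 7.9.7. Sections 7.9.2 and 7.9.10 add a letter (Appendix M) and chemotherapy instructions (Appendix N). Sections 8.4 and 11.4 are not listed.

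**The concern.** The person most likely to see an event first, in a patient treated near home, is given a narrower duty than the protocol places on the trial. An event can be serious or unexpected without being life-threatening. For those events the home physician has no stated deadline, and the listed packet does not carry the rule that would supply one.

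At stake is the investigator-sponsor's duty under 8.4, which cannot be met for an event not yet known at the centre. The two safety reviews in 10.4 (after 10 patients are enrolled, and after the first 10 complete Zevalin) could also run on incomplete data. This matters more here because 10.2 itself describes giving Zevalin soon after chemotherapy as innovative and relies on careful marrow monitoring.

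**Working it through.** The plan gives no figure for this point, so there is none to reproduce. The check is a comparison of the rules, followed by simple arithmetic on delay.

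**1. The rules side by side**

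| | 7.9.7 | 8.4 | 11.4 |
|---|---|---|---|
| Scope | Life-threatening events | Serious or unexpected events; death from any cause | Life-threatening toxicity; unexpected serious toxicity (Grade 3 or 4) |
| Force | Request | Must | Will |
| Time | 24 hours from documentation | Immediately | Immediately |
| In listed packet | Yes, if the evaluation section is Section 7.0 | No | No |

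The material difference is scope. The difference between 24 hours and immediately is slight.

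**2. What falls in the gap.** Serious or unexpected events that are not life-threatening fall outside 7.9.7, and death is not named there. An example is admission for an infection not judged life-threatening. I assume that admission counts as serious; the available text does not define the term. Such events are foreseeable. Section 3.4 cites Grade 3-4 neutropenia in 39/51 = 76% of patients given rituximab with fludarabine, and 2.4 cites Grade 4 neutropenia in 30% after Zevalin. These are laboratory rates, not admission rates.

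**3. When other channels would reveal such an event during R-FND.** Inputs:
- Cycle length (5.6.3): "R-FND courses are recommended to repeated every 28 days".
- Accrual of 2 patients per month, maximum 50 (10.1). Check: 50 / 2 = 25 months, as stated there.
- Toxicity is recorded before each course (8.3).
- Dose or schedule changes need the centre's prior approval (7.9.4).
- Full re-evaluation follows two and four courses (7.2).
- Return visits are at least every 2-3 cycles (7.9.8).

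Formula: further entries = 2 x days / 30.4375.

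| Channel | Delay | Entries meanwhile |
|---|---|---|
| Next course (8.3, 7.9.4) | 1 x 28 = 28 days (4 weeks) | 1.84 |
| Re-evaluation after two courses (7.2) | 2 x 28 = 56 days (8 weeks) | 3.68 |
| Return visits alone, at 3 cycles (7.9.8) | 3 x 28 = 84 days (12 weeks) | 5.52 |

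The last row is an outer bound. In a standard four-course phase, 7.2 does not allow 12 weeks without assessment.

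**4. After R-FND.** Zevalin starts about 12-16 weeks after the last course (5.4.3), which is 3-4 cycle lengths with no course. Section 7.2 then sets re-evaluation 6-8 weeks after Zevalin and again 3 months later. The weekly blood counts in 7.7 give laboratory contact, not event reports. Maintenance rituximab is given every other month (5.5.2). If each dose counted as a cycle (an assumption, since the text does not say), 2-3 cycles would be 4-6 months, or 8-12 entries while accrual is open.

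**5. Scale.** The delay applies only to patients managed outside. Their share is not stated.

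**The case against.** The strongest reply is that the protocol has other channels.

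- **Dose rules.** Sections 5.1.7, 5.6.1, 5.6.2 and 5.6.5 call for dose changes or stopping after infection with neutropenia, neutropenic fever and other severe toxicity, and 7.9.4 requires the centre's approval of any change in dose or schedule. Together with 8.3 and 7.2, these should bring most R-FND-phase events to light by about the next course. This stands, and it is why 4 to 8 weeks is the fair range there. It does not cover events after the last course or those that prompt no change, and it is slower than 8.4 requires.
- **Unseen appendices.** Appendices A, G, M and N are not in the text available. Appendix M is the physician letter in 7.9.2 and 7.9.10, yet 8.4 cites it for adverse event information. The letter may contain the full rule, so any statement about what home physicians are told is conditional. Even a complete letter would leave 7.9.7 narrower than 8.4 and 11.4 within the same packet.
- **Reach of 8.4.** It names no reporter and exempts no one, so the duty still binds the trial. That stands, but a physician who has not been given the rule cannot be relied on to apply it.

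A reader might infer two stronger consequences. The first is that the safety hold acts late, since 10.2 says that "if 2 or more treatment related deaths occur, the study will be temporarily placed on hold". The documents do not show this: a treatment-related death would usually be preceded by a life-threatening event that 7.9.7 already covers. A sudden death, or one not at first linked to treatment, could arrive late, but that is only a possibility. Nor do the entry counts above measure a delayed hold, because non-fatal events trigger no numeric rule. The second is that toxicity is under-counted. Sections 7.9.6 and 8.3 require hospitalization records, progress notes and recording of all toxicities, so late receipt is shown and omission is not.

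**Conclusion.** The point holds as an inconsistency in reporting scope. A serious but not life-threatening event in an outside-managed patient has no stated deadline from the home physician, while 8.4 requires immediate reporting. The likely delay during R-FND is about 4 weeks (roughly 2 further entries), or up to 8 weeks (roughly 4 entries) if the event surfaces only at the re-evaluation after two courses. After R-FND the cycle-based limit is undefined or longer.

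The consequence is delay to the investigator-sponsor's own reporting and possibly incomplete data at the two safety reviews. No sample size, event count or operating characteristic changes. The conclusion assumes 28-day cycles, accrual at 2 per month, and no fuller reporting instruction in the unseen appendices. The conflict in wording is certain; what home physicians are actually told is not, so confidence in the practical effect is moderate.

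**What to change.** - Reword 7.9.7 to the scope of 8.4 and 11.4: the home physician must report every serious or unexpected event, and any death whatever the cause, to the centre's investigator immediately and no later than 24 hours after learning of it. Naming unplanned hospital admission would remove doubt about the commonest case.
- Add the 8.4 reporting text to the items listed in 7.9.5 and 7.9.11.
- Confirm that the Appendix M letter carries the same wording or align it, and reconcile the two uses of Appendix M in 7.9.2/7.9.10 and 8.4.

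The cost is an amendment of protocol and letter wording. The downside is a few more reports from local physicians. Design, sample size and analysis are unaffected.

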# 8.0 Criteria for Response and Toxicity

8.1 Tumor Measures Protocol

a. Lesions will be measured bidimensionally in centimeters prior to each course of therapy. Masses detected by CT may be measured volumetrically in cubic centimeters.

b. The longest diameter and its perpendicular will be measured on bidimensionally measured lesions. Size will be reported as the product of the diameters.

c. Measurements should be made by the radiologist and/or clinician and recorded by the oncology research nurse under his/her supervision.

d. An estimate of overall objective and subjective response will be made and recorded at each visit.

8.2 Response Definitions (34):

I. A molecular complete remission is defined as a patient with an initially positive peripheral blood PCR who converts to negative on at least 2 consecutive occasions no less than 2 months apart. If, during the interval when 2 consecutive blood PCR's are negative, marrow PCR is positive, such patients would not be considered a molecular complete responder. (Such cases of discordance are infrequent but can occur).

II. Clinical CR: defined as those who achieve a normal state which includes no detectable evidence of disease on x-rays.

III. CRu: defined as "CR unconfirmed" on the basis of minimal residual abnormalities on x-ray such as a residual mass <25% of original measurement, and or residual indeterminate bone marrow aggregates.

IV. PR: a 50% or more reduction in the sum of the products of the diameters of the 6 largest measurable lesions. No new sites of disease.

V. Minor response or failure includes < 50% tumor shrinkage or > 50%, but with tumor regrowth between courses. Progressive disease (PD) is also defined by the appearance of new lymph nodes, of other new or worsening sites of disease, such as  $\geq$  50% increase in the size of liver and/or spleen, or a  $\geq$  50% increase in absolute number of circulating lymphocytes. An unimproved bone marrow, i.e., failure too attain the criteria for PR as defined above, will also be considered to be a failure/non-response (NR).

8.3 All toxicities encountered during the study will be evaluated according to the grading system (0-4) in Appendix B and recorded prior to each course of therapy. Duration and treatment will be recorded.

8.4 **Reporting of Serious Adverse Events to the Principal Investigator, the IRB and, if necessary, the FDA** any serious or unexpected adverse event (including death) due to any cause whether or not related to the study drug(s) must be immediately reported to the principal investigator.

It is the responsibility of the Investigator-Sponsor as the IND holder to **IMMEDIATELY REPORT ALL SERIOUS OR UNEXPECTED ADVERSE EVENTS IMMEDIATELY TO THE IRB CHAIR (AS PER INSTITUTION POLICY) AND, IF APPROPRIATE, TO THE FDA BY COMPLETING AND SUBMITTING A MEDWATCH FORM (FDA FORM 3500A).** The Investigator-Sponsor must promptly provide a copy of the MedWatch form to IDEC Pharmaceutical Corporation at the same time it is submitted to the FDA. **Completed FDA 3500A reports should be faxed to the Pharmacovigilance Department of IDEC Pharmaceuticals Corporation [contact]).** See Appendix A and M for additional information and a blank copy of the MedWatch form.

Serious adverse events occurring after initiation of other anti-cancer therapy do not need to be reported, unless the therapy is initiated and the event occurs within 30 days following the infusion of the study drug or the event is felt to be related to the study drug. All written IND Safety Reports submitted to the FDA by the Sponsor-Investigator must also be faxed to:

Genentech Drug Safety [contact] [contact] or [contact]

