5.4.3.5 Evaluations During the In Zevalin Imaging Period

During the imaging period, vital signs will be obtained every 15 minutes for the first hour during the Rituxan infusion, hourly during the remainder of the infusion, and immediately following the indium labeled Zevalin infusion. If vital signs are unstable, they will be monitored at 5-minute intervals until stable.

The purpose of the indium labeled imaging is two fold:

- To evaluate biodistribution of whole body gamma camera images
- To assess whether biodistribution is acceptable to proceed with 90Y Zevalin radioimmunotherapy.

The biodistribution of 111In Zevalin is to be determined from a visual evaluation of whole body gamma images during the first day (2-24 hours) and the second or third day (48-72 hours) after injection.

The expected biodistribution is as follows:

- Easily detectable uptake in the blood pool areas (including but not limited to the heart, major abdominal blood vessels, vascular areas of the head, lungs and pelvis) on the first day image, with less activity in the blood pool areas on the second or third day image.
- Moderately high to high uptake in normal liver and spleen during the first day and the second or third day images.
- Moderately low or very low uptake in normal kidneys, urinary bladder, and normal bowel on the first day image and the second or third day image.
- Tumor uptake may be visualized in soft tissue as areas of the increased intensity, and tumor bearing areas in normal organs may be seen as areas of increased or decreased intensity.

Altered biodistribution would be as follows:

- Diffuse uptake in normal lung more intense than the cardiac blood pool on the first day image, or more intense than the liver on the second or third day image.
- Kidneys with greater intensity than the liver on the posterior view of the second or third day image.

Biodistribution of 111In Zevalin should be assessed on the first day image and second or third day image. If desired, a third image can be obtained at 90 - 120 hrs to support the decision. If the patient has an altered biodistribution, the patient will be taken off study before proceeding to 90Y Zevalin radioimmunotherapy. (See Appendix I for additional details regarding data acquisition for 111In Zevalin).

5.4.4 Subsequent monitoring:

- For toxicity: see sections 7.7 (CBC, etc) and 7.6 (marrow cytogenetics), and Appendices A and L.
- For efficacy: see section 7.2 and 7.3

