6.7.3 Recommended: PET scan

6.8 Any additional appropriate radiologic and radioisotopic examinations should be performed as indicated. **7.0 Evaluation During Study (see Appendix E)**  7.1 Recommended: Patients are recommended to be followed with CBC, platelet count and differential weekly for the first course, and q 2 wk thereafter. An SMA is recommended every month during chemotherapy.

7.2 After two courses, after four courses, 6-8 weeks after Zevalin, (i.e. approximately month 8 and 9), and 3 months later (approximately month 11-12), a full re-evaluation is to be performed, including:

7.2.1 Mandatory: CBC, differential, and platelet count, SMA-12, bone marrow aspiration and biopsy, CT scan of abdomen and pelvis, chest x-ray, and any other studies that were positive at baseline, such as CT head and neck or CT chest.

7.2.2 Optional: quantitative immunoglobulins. Surface marker studies on peripheral blood and bone marrow.

7.2.3 Prior to Zevalin therapy:

- CBC, chemistries, marrow, CXR; and
- Optional: Serum rituximab level

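### Does the lymphocyte criterion in 8.2 V turn normal count recovery into a progression event for TTP?

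*Combined protocol and SAP*

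**What the plan says.** Section 8.2 V is the only definition of progressive disease in the supplied text. It names new lymph nodes and then "other new or worsening sites of disease, such as" two examples: enlargement of liver or spleen by at least half, and a "50% increase in absolute number of circulating lymphocytes" of at least that size. Neither example has a stated reference value.

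Other sections bear on how the clause is applied:

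- 8.1 d: "An estimate of overall objective and subjective response will be made and recorded at each visit".
- 5.4.4, monitoring after Zevalin, separates two purposes: "For toxicity: see sections 7.7 (CBC, etc) and 7.6 (marrow cytogenetics") and "For efficacy: see section 7.2 and 7.3".
- 7.2.1 requires at each full re-evaluation "CBC, differential, and platelet count, SMA-12, bone marrow aspiration and biopsy, CT scan of abdomen and pelvis, chest x-ray", plus any study that was positive at baseline.
- 7.3.2 refers to clinical progression as shown by imaging, marrow and physical examination.
- 11.1 requires the physician to have assigned a tumor response and a toxicity grade; 11.3 makes the Study Chairman final arbiter of disagreements.
- 10.5 censors TTP at last follow-up when progression has not been observed, and stops accrual if Pr(new median > standard median + 12 months) falls below 0.03. Section 10 has no separate definition of progression.

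**The concern.** A percentage rise means little without a base, and the base is least stable when the earlier count is low. This regimen makes counts low. Section 3.4 reports grade 3-4 lymphopenia in 40% of patients given rituximab, and 3.5 says rituximab is given before Zevalin to clear peripheral B lymphocytes. Recovery is expected, and counts are frequent: 7.1 recommends "CBC, platelet count and differential weekly for the first course, and q 2 wk thereafter", with more in 7.7 and 7.8.

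Take assumed counts for illustration. A restaging value of 0.8 x10^9/L is 60% above a previous 0.5 but 20% below a baseline of 1.0. Taken out of its sentence, the clause makes that visit progression or not according to an unstated choice. Limiting assessment to the 7.2 restagings does not remove the ambiguity, because each one includes a differential count.

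At stake is the primary endpoint of a single-arm trial judged against a historical 24 months. False events would shorten the Kaplan-Meier median and make the 10.5 rule more likely to end accrual on a regimen that works. The bias runs one way: it cannot manufacture a success.

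**Working it through.** **1. The text.** The lymphocyte item follows *such as* and is therefore an example of a new or worsening site of disease. Recovering normal lymphocytes are not a site of disease. The item has a natural use: 5.1.1 makes special provision for leukemic patients, in whom circulating cells are disease. Section 5.4.4 puts blood counts under toxicity and efficacy under 7.2 and 7.3. Section 7.3.2 does not list blood counts among its clinical criteria. Section 11.1 makes response a physician's designation, not an automatic result of a laboratory value. At the 7.2 restagings that physician also has marrow and CT. To miscode recovery, the physician would have to call an isolated count rise progression against that evidence.

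**2. The stopping model.** Inputs from 10.5: inverse gamma priors on the medians, with mean 24 and variance 16.7 (standard) or 100 (new). With shape a = mean²/variance + 2 and scale b = mean × (a − 1):

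- Standard: a = 576/16.7 + 2 = 36.49; b = 24 × 35.49 = 851.8.
- New: a = 576/100 + 2 = 7.76; b = 24 × 6.76 = 162.24.

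For exponential TTP with d events in T patient-months, the posterior for the new median is IG(7.76 + d, 162.24 + ln 2 × T).

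**3. The plan's own figure.** Sections 10.4 and 10.5 state 0.054 early stopping at a true median of 36 months. Simulating the rule as written, with a check before each entry, gives 0.173. Omitting ln 2 gives 0.042, the nearest model variant, although it does not match the other rows of the 10.4 table. The program actually used is therefore uncertain, and both versions are shown below. The present point does not depend on which is right.

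**4. False events needed at one look.** Accrual is 2 per month, the true median is 36, and follow-up is 0.5, 1.0, ..., 0.5(n − 1) months at entry of patient n. T is held fixed when false events are added.

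| Look | T | Expected events | With ln 2 | ln 2 omitted |
|---|---|---|---|---|
| Patient 25 | 138.9 | 2.67 (use 3) | d = 3, 4, 5, 6: 0.144, 0.085, 0.048, 0.025 | d = 3: 0.265; d = 7: 0.038; d = 8: 0.021 |
| Patient 40 | 344.9 | 6.64 (use 7) | d = 7, 11, 12: 0.198, 0.034, 0.020 | d = 15, 16: 0.033, 0.020 |

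False events needed to fall below 0.03:

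- Patient 25: 6 − 3 = 3 or 8 − 3 = 5. Of 24 patients already entered, that is 12.5% or 20.8%.
- Patient 40: 12 − 7 = 5 or 16 − 7 = 9. Of 39 patients, that is 12.8% or 23.1%.

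**5. Kaplan-Meier median.** If k of 50 patients are falsely scored before the median, independently of true TTP, the observed median is 36 × [1 + log2(1 − k/50)]. For k = 1, 3 and 5 this is 34.95, 32.79 and 30.53 months. For k = 0 it is 36.

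**The case for a change.** The strongest reply is that context suggests the intended reading without stating it. The 8.2 V sentence gives no test for attributing a rise to lymphoma. Section 7.3.2 concerns when to pursue transplant, not how TTP is scored. Section 11.3 applies only where opinions differ. Surface markers are optional (7.5), and about 85% of patients have the bcl-2 rearrangement (2.2), so PCR cannot settle every case. Setting the clause aside patient by patient is a judgement in an open trial.

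The single-look counts in the working also understate the hazard, because the rule is applied before each entry. Suppose 5% or 10% of patients were miscoded, at times uniform over months 4-12. Simulated early stopping at a true 36 months would rise from 0.17 to 0.28 or 0.41 with ln 2, and from 0.04 to 0.07 or 0.11 without it. With miscoding in months 1-6 the figures are 0.37 or 0.59, and 0.12 or 0.25.

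The arithmetic stands, and so does the gap in wording. What is missing is evidence that miscoding would happen. The 5% and 10% are assumptions. The 40% lymphopenia figure describes depletion, not how often recovery is called progression. The frequent counts in 7.1, 7.7 and 7.8 are not progression assessments. The source cited for the 8.2 definitions is unavailable here, so whether it supplies a comparator is unknown.

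**Conclusion.** The concern does not call for a change. Section 8.2 V leaves the reference count unstated and does not expressly set aside normal recovery, but its own sentence ties the criterion to disease. Sections 5.4.4, 7.3.2 and 11.1 point the same way. A physician following the plan would attribute the rise before calling progression, with marrow and CT available at restaging. The choice of reference then matters only where circulating lymphocytes are lymphoma, and there mainly for dating the event. Writing this into 8.2 V and Section 10 would record the reading already intended.

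The size is not estimable from the documents and is zero without miscoding. If miscoding occurred, it would act against the regimen, and at a single look it would take 3 to 5 false events at patient 25 or 5 to 9 at patient 40 to cross 0.03. Those counts rest on exponential TTP, a true median of 36 months, accrual of 2 per month, average data at each look, and uncertainty over the ln 2 factor. The conclusion rests on response being assigned by a physician, as 11.1 requires. It would be different if TTP events were derived automatically from laboratory counts, which nothing in the plan suggests.
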